## 6.6.2 Storage and Accountability

The Investigator or a designated study collaborator will be responsible for the storage and accountability of the *IQOS* devices and HeatSticks to be distributed only once at V3, together with the device. The *IQOS* devices (charger and holder) as well as HeatSticks (to be distributed only once at V3, together with the device) will be stored in a secured storage site with access limited to authorized personnel only.

A sufficient number of *IQOS* starter kit will be stored at site, to be delivered to subjects allocated to the two *IQOS* arms only. A few additional devices will be stored in case a subject needs to have his/her *IQOS* device replaced. Full accountability of the distributed *IQOS* starter kit and replacement devices, if any, will be ensured by the designated study collaborator and recorded in IP accountability logs. This includes but is not limited to the record of the device serial number, HeatSticks batch number, the quantity of devices and HeatStick packs delivered per subject, date of delivery, total quantity available at site, the quantity of devices returned to the site at the end of the study.

Except for the initial packs of HeatSticks delivered within the *IQOS* starter kit at V3, neither HeatSticks nor cigarettes will be stored at site during the study as they will be bought by the subjects throughout the study.

## 6.6.3 Investigational Product Retention

The subjects will return the *IQOS* device (Charger and Holder), including replacement devices to the study site at V43 or upon early discontinuation. The study site will return to the Sponsor or authorized representative the *IQOS* device (Charger and Holder) upon study completion. This does not apply to devices purchased by the subjects.

# 6.6.4 Adherence to Investigational Products and Reference Arm

Adherence to the allocated product or reference arm will be monitored using self-reported tobacco and nicotine containing product use as reported in the product use diary (Section 7.11.8).

Data and information contained in this document are considered to constitute trade secrets and confidential commercial information, and the legal protections provided to such trade secrets and confidential information are hereby claimed under the provisions of applicable law. No part of this document may be publicly disclosed without the written consent of Philip Morris Products S.A

Philip Morris Products SA	Clinical Study Protocol	Confidential
P1-EXC-01-EU	Version 3.0 / 2 May 2019	Page 58 of 151

# 6.7 Restrictions

## 6.7.1 Product Use Restrictions

There will be no restriction on allocated product use.

# 6.7.2 Dietary Restrictions

Subejcts will be asked not to consume any caffeine- or alcohol-containing products 12 h prior to VO2max and exercise capacity test.

Before safety laboratory and biological health markers blood collections at V3, V14, V28, V43 and V44 subjects will be required to fast for at least 8 h.

# 6.8 Concomitant Medication

Medications will be allowed and carefully monitored during the study by the Investigator or designee. The Investigator or designee is responsible for the medical care including medication of the subjects during their participation in the study. Any decisions regarding the prescription of medication will be taken in the best interest of the subject. The use of any concomitant medication must be fully documented in the source document and transcribed into the CRF. All medication taken within 4 weeks prior to the ICF signature will be considered prior medication. All medication taken from screening visit to end of the safety follow-up period will be considered concomitant medication.

Records of medication taken include the drug name (preferably both generic and trade name), route of administration (e.g., oral, intravenous), total daily dose/unit (e.g., expressed in mg, mL or IU), indication, the start and if applicable, the stop date (day, month and year). Any therapy changes (including changes of regimen) during the study have to be documented.

# 7 STUDY PROCEDURES

Personnel performing or recording study measurements must have appropriate and fully documented training. Quality control (QC) measures must be defined, implemented and documented. All study procedures are provided as an overview in the schedule of events (Appendix 1).

In this section, only the expected/planned time points for the various measurements are given. Considering that not all study participants can have a procedure at the same time point, adequate time windows are given for each study procedure and each time point in Section 9. Site personnel will adhere to the site's standard operating procedures (SOPs) for all activities relevant to the quality of the study. Appropriate medical advice will be provided to the subjects in case of any medical findings requiring health care.

# 7.1 Informed Consent

Prior to any study assessment being performed, the subjects will be asked to provide his/her written consent to participate to the study (ICF) (Section 1.3.). During the consent process, the Investigator or designee obtaining consent must inform each subject of the nature, risks and benefits of, and alternatives to study participation. In addition, each subject must review the ICF and must have sufficient time to understand and have adequate opportunity to ask questions. The ICF must be signed and dated (date and time) prior to undertaking any study specific procedures. A copy of the signed ICF must be given to the subject.

Subjects will be invited to participate in an optional sub-study assessing health and functioning through qualitative interviews (Section 7.11.9) and will sign a separate section of the ICF if they wish to participate.

In addition to the ICF for study participation, the subject will be asked to provide his/her separate optional consent for the collection and storage of samples for long-term biobanking.

# 7.2 Information on the Risk of Smoking and Smoking Cessation Advice and Debriefing on *IQOS*

All subjects included in the study will be advised that the best way of preventing the development of smoking-related diseases is to stop smoking. Only subjects who are not planning to quit smoking cigarettes will be eligible for the study.

From V1 onwards, information on the risks of smoking and smoking cessation advice will be given to all subjects (Appendix 1). This will take the form of a brief interview according to WHO recommendations (54). In addition, a debriefing of subjects will be done to address any intended or unintended beliefs participants have about *IQOS*. The goal of the debriefing is to

Data and information contained in this document are considered to constitute trade secrets and confidential commercial information, and the legal protections provided to such trade secrets and confidential information are hereby claimed under the provisions of applicable law. No part of this document may be publicly disclosed without the written consent of Philip Morris Products S.A

Philip Morris Products SA	Clinical Study Protocol	Confidential
P1-EXC-01-EU	Version 3.0 / 2 May 2019	Page 60 of 151

ensure that subjects have an accurate understanding of *IQOS* risks including an understanding that *IQOS* has not yet been demonstrated to be less harmful than cigarettes.

Any enrolled subject, who is willing to attempt quitting during the study will be encouraged to do so and will be referred to appropriate medical services.

# 7.3 Questions on Smoking History/Habits and Plan to Quit Smoking.

Subject will be questioned for their smoking history and self-reported current tobacco and nicotine containing product use over the past 12 months at V1. The subject will also be asked if he/she is planning to quit smoking within 6 months after V1. This information will be used to assess their eligibility for the study.

# 7.4 Demonstration of *IQOS*

*IQOS* including HeatSticks will be presented to all subjects by the Investigator or designated study collaborator at V1.

# 7.5 Clinical Assessments

## 7.5.1 Demographic Data

Demographic data (sex, date of birth, race) will be recorded at V1.

## 7.5.2 Medical History, Concomitant Disease, Previous and Ongoing Medications

Relevant medical history and any concomitant disease will be documented at V1. Medical history is defined as any condition that started and ended prior to ICF signature. A concomitant disease is defined as any condition that started prior to ICF signature and is still ongoing at V1. The final status of any concomitant disease (i.e stop date or ongoing) should be verified at each visit.

Prior medication taken within 4 weeks prior to screening and any ongoing medication at screening needs to be documented. Any medication which is started prior to screening and is still being taken by the subject at screening or thereafter will be considered as concomitant medication. Medication initiated after the screening visit will also be referred to as concomitant medication. This applies to both prescription and over-the-counter products. If the use of a concomitant medication cannot be avoided for the subject's safety, it must be fully documented in the Source Document and CRF (see Section 6.8).

## 7.5.3 Physical Examination

A full physical examination will include review of general appearance, skin, head, eyes, ears, nose and throat, thyroid gland, chest, lungs, back, abdomen, dentition, cardiovascular, gastrointestinal, musculoskeletal and neurological systems. The physical examination is to be conducted by the Investigator or a designated fully trained representative.

## 7.5.4 Body Height, Weight and Body Mass Index (BMI)

Body height and weight will be recorded and BMI will be calculated using the following formula:

The BMI will be used to assess eligibility for enrollment at V1.

The fat-free weight is defined as:

Weight will be recorded throughout the study (Appendix 1).

## 7.5.5 Vital Signs

Systolic and diastolic blood pressure, pulse rate and respiratory rate will be recorded. All measurements will be made in supine position after the subject has rested for at least 5 minutes in a supine position. The subject should have abstained from smoking or using *IQOS* for at least 15 minutes prior to measurement.

## 7.5.6 Spirometry

All personnel performing spirometry testing must have the appropriate training with the record of the training. Quality control measures should be available and be properly documented.

Data and information contained in this document are considered to constitute trade secrets and confidential commercial information, and the legal protections provided to such trade secrets and confidential information are hereby claimed under the provisions of applicable law. No part of this document may be publicly disclosed without the written consent of Philip Morris Products S.A

Philip Morris Products SA	Clinical Study Protocol	Confidential
P1-EXC-01-EU	Version 3.0 / 2 May 2019	Page 62 of 151

The spirometry test will be performed in accordance with the 2005 guideline of the American Thoracic Society (ATS)/European Respiratory Society (ERS) Joint Task Force on the standardization of spirometry (55).

Pre and post- bronchodilator spirometry assessments will be performed. Each assessment requires at least three valid spirometry tests. The ratio of forced expiratory volume in one second (FEV1) / forced vital capacity (FVC) will be calculated from the highest acceptable FEV1 and the highest acceptable FVC, respectively.

The results from FEV1 and the ratio FEV1 to FVC at V1 will be used for eligibility criteria to assess COPD and asthma conditions. All spirometry testing will be recorded in sitting position after resting for at least 15 minutes in sitting position. The subject should have abstained from smoking or using *IQOS* for at least 1 hour prior to testing. All post-bronchodilator spirometry testing will be performed 15-30 minutes post administration of around 400  $\mu$ g of salbutamol/albuterol (usually equivalent to 4 puffs assuming 100  $\mu$ g/puff). The time of salbutamol/albuterol inhalation and time of spirometry assessment will be recorded in the source document.

## 7.5.7 Electrocardiogram

ECG testing will be performed as per the site's local practice. A standard 12-lead ECG will be recorded after the subject has rested for at least 10 minutes in a supine position.

The following parameters will be documented: heart rate, PR interval, QRS interval, QT interval, and QT interval corrected according to Bazett's formula and Fridericia's formula. Every ECG has to be assessed as normal, abnormal – clinically not relevant, or abnormal – clinically relevant. A diagnosis has to be provided on the CRF for all ECGs assessed as abnormal – clinically relevant. All ECG print-outs will be interpreted by a qualified physician. Any print-outs of ECGs on thermo-sensitive paper must be photocopied.

## 7.5.8 Body-fat Percentage and Waist Circumference

Body-fat percentage based on skinfold caliper measurements and waist circumference will be performed as per the site's practice. Mesurements should be performed by the same trained site collaborator and using the same instrument.

## 7.5.9 Determination of Blood Composition and Volume

Hemoglobin mass ( $Hb_{mass}$ ) will be quantified using an automated system (e.g. OpCO, Detalo Instruments, Denmark or similar). First, a venous blood sample will be drawn to measure hemoglobin, hematocrit and COHb, after which the CO re-breathing procedure will be performed. Using the system a precise volume of CO is inhaled and re-breathed by the subject

Data and information contained in this document are considered to constitute trade secrets and confidential commercial information, and the legal protections provided to such trade secrets and confidential information are hereby claimed under the provisions of applicable law. No part of this document may be publicly disclosed without the written consent of Philip Morris Products S.A

Philip Morris Products SA	Clinical Study Protocol	Confidential
P1-EXC-01-EU	Version 3.0 / 2 May 2019	Page 63 of 151

for 10 min. During the re-breathing period 100% O2 is administered to the subject on a demand basis, and due to the small volume of CO administered and the continuous O2 supplementation arterial O2 is barely affected. After completion of the re-breathing procedure COHb will be measured again. Then based on the resulting increase in COHb, the mass of hemoglobin will be calculated. Red blood cell volume, plasma volume and blood volume will be derived from measures of Hbmass, [Hb] and hematocrit.

# 7.6 Exercise Testing and Training

## 7.6.1 VO2max Test and Blood Lactate Levels

Subjects will perform an incremental cycling test to volitional fatigue on an electronically braked cycle ergometer (such as Monark E839, Varberg, Sweden). To measure oxygen uptake and determine VO2max an online gas collection system (e.g. COSMED CPET) will be used where O2 and CO2 concentration in the expired gas are continuously measured and monitored as breath-by-breath values.

Subjects will be asked to refrain from heavy exercise 24h prior to the test, and consuming caffeine or alcohol 12h prior to the test. Measurements will begin with the subjects resting for 3 min seated on the bike ergometer whereafter the workload will be increased by 25W every 60 sec until volitional fatigue. Subjects should keep cadence between 60 and 90 rpm during the test. Mean VO2max will be determined as the highest O2 value averaged over 30 s for each subject. At VO2max the following parameters will be recorded: ventilation (l/min) respiratory rate, VCO2 (l/min), respiratory exchange ratio (RER, [VCO2 / VO2]).

In addition at V4, the maximal heart rate and the maximal work rate will be recorded in order to design the training program.

At V3 and V43, capillary (fingertip or earlobe) blood samples will be obtained at rest and at each 25W workload increased and analysed for lactate (e.g. Radiometer ABL80 or similar). Blood collection should be started 40-45 seconds into the workload and no blood sample should be obtained at maximal effort. The final blood sample should be obtained within 5 minutes after termination of the bike exercise. Heart rate and oxygen uptake (VO2) will be recorded at rest at each 25W increase.

After the test subjects will rest for  $60\pm5$  min and will be offered water *ad libitum* and a light snack e.g. fruit, chocolate or bar. The snack has to be consumed at least 30 min before the upcoming exercise capacity test (not applicable for V1).

Data and information contained in this document are considered to constitute trade secrets and confidential commercial information, and the legal protections provided to such trade secrets and confidential information are hereby claimed under the provisions of applicable law. No part of this document may be publicly disclosed without the written consent of Philip Morris Products S.A

## 7.6.2 Exercise Capacity Test

Subjects will perform an exercise capacity test during which they will complete a given workload as quickly as possible. The criteria for completion of the test is the completing of a pre-defined relative work determined based on the highest wattage level reached at VO2max test times 1.25 (i.e. 200 W x 1.25 = 250; 250 kcal to be completed). The highest wattage reached at the VO2max test at V1 will be used for the test at V2, and at the VO2max test V3 will be used for the tests at V3, V4 and V43. This relative workload determination is selected for the exercise capacity tests because it i.) controls for differences in baseline aerobic capacity across subjects, and ii.) standardizes the time of completion of all baseline tests at approximately 20 minutes.

## 7.6.3 Exercise Training

Subjects randomized into the *IQOS*-1, cigarette and SA arms will participate in a 12-week training program consisting of 38 training sessions (V5-V42). All training sessions will be performed at the investigational site using stationary bikes, and will be supervised by designated site personnel.

Different training programs will be circulated to provide the study participants with differentiated training inputs and make the training sessions less monotonous. Each training session will last 40 min with a training intensity ranging between 60-85%. The target exercise heart rates are based on the subject's resting (HRrest; obtained during ECG at V3) and maximal heart rate (HRmax) obtained during the acute effect VO2max test at V4. The formula to be used for exercise heart rates is: Target exercise heart rate = ((HRmax – HRrest) \* intensity) + HRrest with intensity as fraction of 1.

## 7.7 Biomarker Assessment

### 7.7.1 Exhaled Carbonmonoxide (CO)

Carbon monoxide (CO) in exhaled breath will be measured using the a Smokerlyzer® device, such as the Micro 4 Smokerlyzer® or similar. At V1 and V2, a cut-off of >6 ppm for confirming cigarette smoking status will be applied (56)(57).

### 7.7.2 Carboxyhemoglobin (COHb)

Venous blood samples will be collected and COHb measured by a designated laboratory.

Data and information contained in this document are considered to constitute trade secrets and confidential commercial information, and the legal protections provided to such trade secrets and confidential information are hereby claimed under the provisions of applicable law. No part of this document may be publicly disclosed without the written consent of Philip Morris Products S.A

Philip Morris Products SA	Clinical Study Protocol	Confidential
P1-EXC-01-EU	Version 3.0 / 2 May 2019	Page 65 of 151

# 7.7.3 Urine Biomarkers of Exposure

Spot urine will be collected to measure concentrations of NEQ, NNAL, CEMA and creatinine. The urine collection should be performed as late as possible during the day.

# 7.7.4 Biological Health Markers in Blood

Venous blood samples will be collected for measurement of HDL, LDL, VLDL, hs-CRP, GH and HbA1c (%). Blood samples will be taken after at least 8 hours of fasting (Section 6.7.2).

# 7.8 Laboratory Assessments

# 7.8.1 Clinical Chemistry, Hematology, and Urinalysis for Safety Panel

Hematology, clinical chemistry, serology and urinalysis safety panel will be measured at local laboratory except for urine drug screening, urine cotinine screening,, alcohol breath test and urine pregnancy test, these tests will be performed at site

Blood samples will be taken after at least 8 hours of fasting (Section 6.7.2) except at screening (V1) and early termination. Parameters to be measured are listed in Table 3.

# Table 3 Clinical Laboratory Parameters for Safety Panel

Hematology	Clinical Chemistry	Urinalysis
Hematocrit	Albumin	• pH
Hemoglobin	Total protein	Bilirubin
Mean corpuscular hemoglobin	Alkaline phosphatase (AP)	Glucose
(MCH)	Alanine aminotransferase (ALT)	Nitrite

 
Mean corpuscular hemoglobin concentration (MCHC)
 
	Aspartate aminotransferase (AST)	Red blood cell
Mean corpuscular volume	Blood urea nitrogen (BUN)	traces
(MCV)	Creatinine	Protein
Platelet count	Gamma-glutamyl transferase	Specific gravity
• Red blood cell (RBC) count•	(GGT)	
White blood cell (WBC) count	Glucose	
Differential WBC count:	
 
Lactate dehydrogenase (LDH)
 
	
- Neutrophils	Potassium	
- Basophils	• Sodium	
- Eosinophils	Total bilirubin	
- Lymphocytes	Direct bilirubin	
- Monocytes	Total cholesterol (TC)	
	Triglycerides (TG)	

## 7.8.2 Serology

At V1, a test for hepatitis B (HbsAg), hepatitis C (HCV antibody), and human immunodeficiency virus (anti-HIV1/2) will be performed. In case of positive results, the subject will be referred to appropriate medical care.

## 7.8.3 Urine Drug Screening

At V1 and V2, urine drug screen (amphetamines, barbiturates, benzodiazepines, cannabinoids, cocaine, opiates, methadone, methamphetamines, phencyclidine, tricyclic antidepressants) will be performed by the personnel at the investigational site.

## 7.8.4 Urine Cotinine Screening

At V1 and V2, a urine dip-stick cotinine test with a threshold of  $\geq$  200 ng/mL will be performed at the investigational site to confirm subject's smoking status.

### 7.8.5 Alcohol Breath Test

At V1 and V2, a breath alcohol test will be performed at the investigational site using a breathalyzer device.

## 7.8.6 Urine Pregnancy Test

A urine pregnancy test will be done at the investigational site for all female subjects at V1-V3 V5, V14, V28 and V44.

Subjects with a positive pregnancy test at V1 or at V2 will not be enrolled and will be considered screening failures. In any case of a positive urine pregnancy test, the Investigator will inform the subject about the risks associated with smoking during pregnancy.

All pregnancies detected during the study must be reported and handled as described in Section 8.5. Pregnancies detected after enrollment will lead to discontinuation from the study.

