# 9 STUDY ACTIVITIES

The procedure can be performed at any time during the visit, unless otherwise specified. Assessments will be conducted only by qualified and trained site personnel.

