# 9.2 Enrollment and Familiarization with Exercise Test

Visit 2 (V2) will be scheduled 7±1 days prior to V3 (randomization).

Table 6 shows the procedures that will be performed at V2.

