### **Confidentiality Statement**

Philip Morris Products SA	Clinical Study Protocol	Confidential
P1-EXC-01-EU	Version 3.0 / 2 May 2019	Page 84 of 151

Time	Blood Sample	Procedures	Additional Information
Start of Procedure		V2	
Prior to enrollment		Collection of spot urine for: • Urine cotinine test • Urine drug screen • Urine pregnancy test Confirmation of smoking status by CO breath test. Alcohol breath test	Confirmation of eligibility. Has to be done in the morning prior to enrollment
		Enrollment	
After enrollment		Vital signs (blood pressure, pulse rate, respiratory rate)	After resting for at least 5 minutes in supine position
		Information on the risk of smoking, smoking cessation advice	
		Exercise capacity test – bike ergometer	Work to complete will be based on the highest wattage level reached during VO 2 max test during V1. After completing the test water will be provided ad libitum .
		mHealth wearable kit distribution and training on how to wear, handle and charge the device	
		Product use diary distribution	
		Concomitant medication	
		AE/SAE recording	At any time during the day.
Abbreviations.			

Abbreviations:

AE = Adverse event; CO = Carbon monoxide; SAE = Serious adverse event.

During the  $7\pm1$  days between V2 and V3, subjects having signed the optional section of the ICF will have an interview (by phone or computer) on the topic of health and functioning lasting around 60 minutes.

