# 9.3 Baseline and Randomization

Table 7 shows the procedures that will be performed at V3. All baseline assessments should be performed before randomization.

Time	Blood Sample	Procedures	Additional Information
Start of Procedure		V3	
		Urine pregnancy test	
Before breakfast/ snack	$\checkmark$	Clinical laboratory parameters (hematology, clinical chemistry and urinalysis)	At least 8 hours of fasting Hematocrit and Hemoglobin results will also be used to calculate blood volume
	$\checkmark$	Biological health markers	At least 8 hours of fasting
	$\checkmark$	Biobank blood collection	Only if optional ICF signed At least 8 hours of fasting
		Breakfast/Snack	
		Biobank saliva and sweat collection	Only if optional ICF signed
		FTND questionnaire	
		Lifestyle questionnaire	
		RPC scale	
		Vital signs (blood pressure, pulse rate, respiratory rate)	After resting for at least 5 minutes in supine position
		ECG	After resting for at least 10 minutes in supine position prior to recording.
		Physical examination	
		Weight, body fat percentage and waist circumference	
		Cough assessment questionnaire (VAS scale, and 3 Likert scales)	
		CO breath test	

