### Table 11 Time Schedule – V43 Training Effect Exercise Tests

Time	Blood Sample	Procedures	Additional Information
Start of Procedure		V43	
Before breakfast/ snack		Biological health markers	At least 8 hours of fasting
	$\checkmark$	Biobank blood collection	Only if optional ICF signed At least 8 hours of fasting
		Breakfast/snack	

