### **Confidentiality Statement**

Philip Morris Products SA

P1-EXC-01-EU

Clinical Study Protocol Version 3.0 / 2 May 2019

Page 92 of 151

Time	Blood Sample	Procedures	Additional Information
Start of Procedure		V43	
		Biobank saliva and sweat collection	Only if optional ICF signed
		Vital signs (blood pressure, pulse rate, respiratory rate)	After resting for at least 5 minutes in supine position
		Weight,body fat percentage and waist circumference	
		RPC scale	
		CO breath test	
30-60 min before VO 2 max test		Subjects in IQOS -1 and IQOS -2 arms will use a HeatStick. Subjects in the cigarette arm will smoke a cigarette.	Only subjects willing to.
After all clinical assessments		VO₂max test	HR and VO 2 will be recorded at rest and at each 25W increase
During VO₂max test		Borg RPE scale	At rest and at each 25W increase
During VO₂max test	$\checkmark$	Capillary blood lactate sampling to measure lactate levels	At rest and at each 25W increase
After VO 2 max test		Snack and water ad libitum	Snack to be consumed at least 30 min before start of exercise capacity test
60±5min after VO₂max test		Exercise capacity test – bike ergometer	Work to complete will be based on the highest wattage level reached during VO 2 max test at V3. After completing the test water will be provided ad libitum.
After exercise capacity test Before CO- rebreathing	$\checkmark$	СОНЬ	Results will be used to assess 1) CO exposure and 2) to calculate blood volume
After exercise capacity test	$\checkmark$	Determination of blood volume by CO-rebreathing	Blood will be sampled before CO- rebreathing to for Hematocrit and Hemoglobin and after CO- rebreathing for COHb determination

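### No pregnancy test is scheduled at V43 before the VO2max test, exercise capacity test and CO re-breathing; the latest scheduled result is then 34 to 42 days old

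*Protocol*

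**What the plan says.** Protocol section 7.8.6 fixes the testing visits: "A urine pregnancy test will be done at the investigational site for all female subjects at V1-V3 V5, V14, V28 and V44". The visit tables follow it. Table 9, which covers V5 to V42, restricts the test to V5. Table 10 adds it at the medical visits V14 and V28, and Table 12 has it at V44. Table 11, the V43 schedule, has no pregnancy test row; its first entry is "Biological health markers". Appendix 1 and SAP Table 13-1 show the same pattern, with nothing marked from V29 to V43.

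V43 contains three procedures that matter here. In the VO2max test (section 7.6.1), "the workload will be increased by 25W every 60 sec until volitional fatigue". After about an hour's rest comes the exercise capacity test (section 7.6.2), a fixed amount of work done against the clock. Table 11 then lists "Determination of blood volume by CO-rebreathing", in which CO is inhaled and re-breathed for 10 minutes (section 7.5.9).

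The only other visit with CO re-breathing is V3. There, Table 7 schedules a urine pregnancy test on the same day and lists it first.

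Pregnancy is exclusion criterion 10 in section 5.1.2, with Safety as the stated rationale. Section 5.2 makes a positive or unclear test a mandatory reason for discontinuation, and section 7.8.6 repeats that a pregnancy found after enrolment ends participation.

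**The concern.** A discontinuation rule that depends on a test protects a participant only if a test is done before the procedure in question. At V43 none is. If a woman's pregnancy becomes detectable after V28 despite contraception, no scheduled test stands between her and the maximal exercise test, the timed test and the CO inhalation. The V44 test can record the pregnancy, but only after those procedures are over. The longest untested interval after randomisation also ends just after the visit that repeats V3's exercise tests and CO inhalation.

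What is at stake is participant safety at one visit, at low frequency. The VO2max and exercise capacity data are not affected.

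**Working it through.** **Inputs (days after V3).** V5 15±2 (section 4.1); V14 40±2 and V28 68±2 (section 9.4.2); V43 106±2 and V44 107±2 (section 9.4.3).

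**The protocol's own interval.** Section 4.4 puts V44 at 1±2 days after V43. Check: 107 − 106 = 1. Reproduced. The longest allowed gap is 1 + 2 = 3 days.

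**Age of the latest scheduled result at V43.**
- Nominal: 106 − 68 = 38 days.
- Shortest: (106 − 2) − (68 + 2) = 34 days.
- Longest: (106 + 2) − (68 − 2) = 42 days.
- Adding the rule that V43 falls 7±2 days after V42 (day 99±2) still gives 34 to 42.

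**Untested intervals after randomisation.**

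| Interval | Nominal days | Range |
|---|---|---|
| V3 to V5 | 15 | 13–17 |
| V5 to V14 | 25 | 21–29 |
| V14 to V28 | 28 | 24–32 |
| V28 to V44 | 39 | 35–43 |

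The last interval is 39 − 28 = 11 days longer than the one before it.

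**Comparison visits.** At V3 a same-day test is scheduled. V4 has both exercise tests and no same-day pregnancy test, but the V3 result is then only 7 days old (7 − 2 = 5 to 7 + 2 = 9) and no CO is given. V43 is therefore the one visit that combines CO re-breathing with an old result.

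**How often this could matter.** The documents give neither the number of women of childbearing potential (W) nor the yearly contraceptive failure rate (p). I assume W = 10 to 60 of the 90 randomised and p = 1% to 10%. Expected conceptions over d days = W × (1 − (1 − p)^(d/365)).
- W = 10, p = 0.01, d = 34: 0.009
- W = 10, p = 0.01, d = 38: 0.010
- W = 60, p = 0.10, d = 38: 0.65
- W = 60, p = 0.10, d = 42: 0.72

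The range is about 0.01 to 0.72 in the whole trial. The delay before a urine test turns positive shifts this window but does not shorten it, because the V28 test has the same delay. The figure counts all conceptions. It deducts nothing for women who recognise the pregnancy themselves or who leave before V43, so for given inputs it is an upper bound on pregnancies still unrecognised at V43.

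**After the change.** With a test at the start of V43, the age of the latest result falls from 34–42 days to zero.

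**The case against.** The strongest opposing case is that this is a schedule preference with little to gain.

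- **Contraception and contact.** Effective contraception is required until the end of safety follow-up (section 5.1.2). Health is asked about with open questions at every visit: 14 visits from V29 to V42 in the training arms, and V30, V33, V35 and V39 in IQOS-2. Many pregnancies would come to light this way. This stands as a reason for low frequency. It does not supply a test, and the protocol itself requires contraception and still tests at V3, V5, V14, V28 and V44.
- **Harm is not shown.** Section 7.5.9 describes the CO volume as small and arterial oxygen as barely affected. Women in the cigarette arm take in CO daily, and section 2.1.1 gives an expected COHb of 3–15% in smokers. This stands too. The case rests on the protocol's own discontinuation rule, not on a demonstrated harm.
- **The change covers little.** Up to 14 training sessions of 40 minutes at 60–85% intensity would still rely on the V28 result. Moving the test brings detection forward by nominally one day and spares only the V43 procedures. That is correct and limits the benefit.
- **Order at V3.** A reader might infer that the V3 test must always precede the CO, or that it may freely follow it. Neither is settled. Section 9 says "The procedure can be performed at any time during the visit, unless otherwise specified", and section 9.3 adds "All baseline assessments should be performed before randomization". But Table 7 also places the VO2max test after all clinical assessments, and CO re-breathing after the exercise capacity test. Whether a pregnancy test, which sits under laboratory assessments (section 7.8), counts as a clinical assessment is arguable. The comparison needs only that a same-day test is scheduled at V3 and not at V43.

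**Conclusion.** The point holds as a cheap improvement. Before the V43 procedures the latest scheduled pregnancy result is nominally 38 days old (34 to 42), and the next test comes nominally one day afterwards. No scheduled test can trigger the mandatory discontinuation in between. The day counts rest only on the stated visit windows. The conception range of 0.01 to 0.72 rests on assumed values of W and p and bounds the unrecognised cases from above.

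Three stronger readings are tempting, and the documents do not support them:
- That the schedule contradicts itself or lost a row. Section 7.8.6, Tables 9 to 12, Appendix 1 and SAP Table 13-1 all agree, so this is a choice of placement.
- That the V43 CO inhalation or exercise would be harmful in pregnancy. No harm is quantified, and the Safety rationale for excluding pregnant women is not tied to these procedures.
- That the trial's results are compromised. Nothing here touches the endpoints.

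**What to change.** Move the V44 urine pregnancy test to the start of V43 in section 7.8.6, Tables 11 and 12 and Appendix 1, and align SAP Table 13-1 for consistency. State in Table 11 that the result must be available before the exercise tests and CO re-breathing, because section 9 otherwise allows any time during the visit. Keep the early-termination test in section 9.6. Retaining the V44 test as well is optional.

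Costs:
- An amendment submitted to the IEC, implemented only after approval if classed as substantial (section 1.1). It is best bundled with another amendment.
- A CRF change; the SAP cites eCRF version 4.0.
- One early urine sample at V43, separate from the exposure-marker urine, which is collected as late as possible.
- If V44 is dropped, nominally one day and at most three days less end-of-study pregnancy surveillance.

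The test is the same on-site test, so no new procedure is needed. SAP version 2.0 (March 2020) describes parts of study conduct in the past tense, so an amendment may come too late for many participants. The documents do not give recruitment status, so this is inference.
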